1.4 Study Design

This is multi-center two stage phase 2 study to evaluate the clinical activity of retifanlimab in patients with unresectable or metastatic ASQ. This study will enroll subjects who have progressed after at least 1 prior chemotherapy regimen, have been deemed unfit for cytotoxic chemotherapy or who have refused cytotoxic chemotherapy. The primary endpoint of this study will be disease control rate (DCR) at 4 months following the start of treatment using RECIST 1.1. Up to 25 subjects will be enrolled to target 21 evaluable patients.

The study will consist of a screening period (within 21 days of first dose), a treatment period per the table below (**Section 10**), and a follow-up period. Subjects will receive a baseline biopsy and then be treated with the anti-PD1 antibody retifanlimab every 4 weeks. After 2 doses (8 weeks), subjects will be assessed for response with imaging and laboratory tests and receive another research biopsy. For patients with stable disease or tumor response and clinical benefit, retifanlimab will be continued until disease progression or unacceptable toxicity. Patients will be evaluated radiographically after every 2 doses of retifanlimab (every 8 weeks). Subjects will come

to the clinic for dosing and assessments on Day 1 of each cycle. Assessment will consist of 1) physician evaluation to assess symptoms of tumor response or progression and potential drug related toxicity, 2) cross sectional imaging (CT scans), 3) CA19-9 blood levels. Additional visits for safety and immune monitoring follow-up will occur per the study calendar in **Section 10**.

No dose escalations or reductions are allowed. Enrollment will continue until 21 subjects have received at least one dose of retifanlimab and completed one cycle of therapy. The null hypothesis that the DCR 4 months following the start of treatment is 5% will be tested against a one-sided alternative (DCR of 30%).

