- 18: Cycle 1 Day 1 evaluations do not need to be repeated if they were conducted within 3 days of the screening evaluations.
- 19: Day 15 (± 1 day) adverse event assessments may be conducted by telephone or email after cycle 2 day
- 20: Subjects will return to the study site for an EOT evaluation. EOT follow-up will occur 28 (±7) days after the last dose of study drug. NOTE: CT scan assessment at EOT will occur 28 days (± 4 weeks) after the final dose. If the EOT visit occurs early (or if the patient cannot return due to disease progression), an assessment for AEs should be made by telephone or email on day 28 (±1) after last study dose. Subjects who restart study drug after off-treatment progression should have a second EOT visit performed when they stop study drug a second time.
- 21: Subjects who discontinue treatment should be contacted by telephone or email at 90 days (+ 14 day reporting window) from their last dose of study drug or within 7 days before initiation of a new antineoplastic treatment (whichever comes first) to assess for treatment related toxicities. In addition, all SAEs occurring during this time should be reported as well.
- 22: Subjects who discontinue treatment without disease progression should continue to be monitored for disease status by radiologic imaging (Section 5.12.2). Disease monitoring should continue to be assessed every two months (± 2 weeks) for the first 2 years and then every 3 months (± 4 weeks) until: 1) start of a new antineoplastic therapy (information of the new cancer therapy will be collected), 2) disease progression, 3) death, 4) withdrawal of consent, or 5) study closure, whichever occurs first.
- 23: Subjects who discontinue treatment will enter the survival follow-up portion of the trial (**Section 5.12.3**). Subjects should be contacted every 12 weeks (± 2 weeks) to monitor overall survival. Information of other cancer therapies after discontinuation from the study treatment will be collected as well.

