11. STUDY ENDPOINTS

11.1 Primary Endpoint

The primary endpoint is DCR at 4 months following the start of treatment with retifanlimab, which is defined as the proportion of subjects with PR or CR or stable disease according to RECIST 1.1 following 4 months from the start of therapy. Subjects who discontinue due to toxicity prior to post-baseline tumor assessments will be evaluable and considered treatment failures. Otherwise, subjects who discontinue or do not have any post-baseline scans for other reasons including withdrawal of consent or being lost to follow-up prior to C2D1 will be replaced and not included in the primary efficacy analysis.

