11.2 Secondary Endpoints

The secondary endpoints are as follows:

- ORR is defined as the proportion of subjects with PR or CR according to RECIST 1.1. Subjects who discontinue due to toxicity or clinical progression prior to post-baseline tumor assessments will be considered as non-responders. Otherwise, subjects who discontinue or do not have any post-baseline scans for other reasons including withdrawal of consent or being lost to follow-up prior to C2D1 will be replaced and not included in the primary efficacy analysis.
- Progression-free survival (PFS) is defined as the number of months from the first
 dose of retifanlimab to radiographic disease progression (PD or relapse from CR
 as assessed using RECIST 1.1 criteria), documented clinical progression as
 assessed by the treating provider, or death due to any cause. PFS will be censored
 at the date of the last scan for subjects without documentation of disease
 progression at the time of analysis.
- Safety assessed by the following measures:
 - Number of patients who have grade 3 or above drug-related toxicities
 - Frequency of drug-related toxicity by grade
 - Retifanlimab-related infusion reactions
 - Immune-related AEs
 - Unacceptable toxicities
 - Vital signs: BP, pulse, temperature
 - Physical examination
 - Changes in ECG readings
 - Clinical hematology: complete blood count (CBC) with differential ANC,
 ALC, AEC, and platelet count
 - Clinical serum chemistry: sodium, potassium, chloride, bicarbonate, glucose, blood urea nitrogen (BUN), creatinine, lactate dehydrogenase (LDH), ALT, AST, alkaline phosphatase, lipase, bilirubin (total), total protein, albumin, calcium, magnesium and phosphate

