13. STATISTICAL CONSIDERATIONS

13.1 Study Design/Endpoints

Sample Size calculation and justification

Simon's two-stage optimal design will be used ¹⁸. The null hypothesis that the true disease control rate at 4 months is 5% will be tested against a one-sided alternative of 30% disease control rate at 4 months. In the first stage, 7 patients will be accrued. If there are zero patients with disease control by 4 months, the study will be stopped. Otherwise, 14 additional patients will be accrued for a total of 21 patients. The null hypothesis (disease control rate of 5%) will be rejected if 3 or more patients with disease control at 4 months are observed in stage 1 and 2 combined. This design yields a type I error rate of 0.064 (target type I error 0.1) and power of 90% when the true disease control rate is 30%. The probability of stopping the trial early for futility is 70% if the true DCR is 5%.

We plan to enroll 25 subjects to ensure 21 would be evaluable for DCR. As this is a rare tumor subtype patients will be recruited at several sites including Johns Hopkins Hospital, Memorial Sloan Kettering Cancer Center and the Mayo Clinic. We do not anticipate any difficulties in trial enrollment. We expect an accrual rate of at least 2 patients per month across the sites, completing trial enrollment in 12 months.

Patients are evaluable for DCR if they receive at least one dose of retifanlimab, and have at least one post-baseline tumor assessments or discontinue due to toxicity or clinical progression prior to post-baseline tumor assessments. The study plans to enroll 25 subjects to ensure 21 would be evaluable for the primary efficacy endpoint.

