13.2 Data and Analysis Plan

Analysis of Primary Endpoint

The primary endpoint of the study will be disease control (DC) at four months using RECIST 1.1. DC is defined as complete response, partial response and stable disease at 4 months, per RECIST 1.1. Disease control rate (DCR) will be estimated as the proportion of patients who achieve DC at 4 months, along with 95% confidence interval

Analysis of Secondary Clinical Endpoint

The objective response rate defined as the proportion of response evaluable subjects who have a complete response (CR) or partial response (PR) using RECIST 1.1 criteria at any time during the study. The evaluable population includes all subjects who have completed at least one dose of retifanlimab and have received at least one follow-up scan or discontinue due to toxicity or clinical progression prior to post-baseline tumor assessments. Response rate will be reported with exact 95% confidence interval.

Progression-free Survival (PFS) is defined as the time from cycle 1, day 1 of retifanlimab until first documented local progression or death due to any cause. Disease progression will be assessed using RECIST (version 1.1) and/or documented clinical progression as assessed by the treating provider. Due to the expectation that some patients may experience delayed clinical responses to therapy, patients with disease progression by radiographic imaging or laboratory parameters during a 12-week evaluation period but without rapid clinical deterioration or significant change in performance status that requires additional immediate therapy may continue to receive treatment on study. Subjects that meet the above criteria and continue on study therapy must discontinue treatment upon documentation of disease progression on the second scan. The date of progression will be backdated to the time of first RECIST criteria progression. Tumor assessments will be made using RECIST 1.1 and immune RECIST (iRECIST). Individuals will be censored at the date of the last scan prior to initiation of an alternative therapy for PFS if no event occurs before the start of the alternative therapy.

PFS will be summarized descriptively using the Kaplan-Meier method. Analysis of PFS will be restricted to evaluable individuals who complete at least one dose of retifanlimab.

Analysis of Safety Endpoints

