The best overall response is the best response recorded from the start of the treatment until disease progression/recurrence (taking as reference for progressive disease the smallest measurements recorded since the treatment started). The subject's best response assignment will depend on the achievement of both measurement and confirmation criteria.

For Subjects with Measurable Disease (i.e., Target Disease)

Target Lesions	Non-Target Lesions	New Lesions	Overall Response	Best Overall Response when Confirmation is Required*
CR	CR	No	CR	≥4 wks. Confirmation**
CR	Non-CR/Non-PD	No	PR	
CR	Not evaluated	No	PR	\geq 4 wks.
PR	Non-CR/Non-PD/not evaluated	No	PR	Confirmation**
SD	Non-CR/Non-PD/not evaluated	No	SD	Documented at least once \geq 4 wks. from baseline**
PD	Any	Yes or No	PD	
Any	PD***	Yes or No	PD	no prior SD, PR or CR
Any	Any	Yes	PD	

^{*} See RECIST 1.1 manuscript for further details on what is evidence of a new lesion.

Note: Subjects with a global deterioration of health status requiring discontinuation of treatment without objective evidence of disease progression at that time should be reported as "symptomatic deterioration." Every effort should be made to document the objective progression even after discontinuation of treatment.

Reference

E.A. Eisenhauer, P. Therasse, J. Bogaerts, L.H. Schwartz, D. Sargent, R. Ford, J. Dancey, S. Arbuck, S. Gwyther, M. Mooney, L. Rubinstein, L. Shankar, L. Dodd, R. Kaplan, D. Lacombe, J. Verweij. New response evaluation criteria in solid tumours: Revised RECIST guideline (version 1.1). Eur J Cancer. 2009 Jan;45(2):228-47.

^{**} Only for non-randomized trials with response as primary endpoint.

^{***} In exceptional circumstances, unequivocal progression in non-target lesions may be accepted as disease progression.

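### Sections 11.1 and 13.1 disagree on whether unscanned clinical progression counts in the primary DCR, and neither covers death before the first scan

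*Combined protocol and SAP*

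**What the plan says.** Four places define who is evaluable for the tumour endpoints.

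- **Section 11.1 (primary DCR).** "Subjects who discontinue due to toxicity prior to post-baseline tumor assessments will be evaluable and considered treatment failures". The next sentence covers everyone else who discontinues or has no post-baseline scan: those with "other reasons including withdrawal of consent or being lost to follow-up prior to C2D1 will be replaced and not included" in the primary efficacy analysis.
- **Section 13.1 (primary DCR).** A dosed patient is evaluable with at least one post-baseline assessment, or if they "discontinue due to toxicity or clinical progression prior to post-baseline tumor assessments". It does not say in terms that these patients are failures.
- **Section 11.2 (ORR).** "Subjects who discontinue due to toxicity or clinical progression prior to post-baseline tumor assessments will be considered as non-responders".
- **Section 13.2 (ORR population).** Dosed subjects who "have received at least one follow-up scan or discontinue due to toxicity or clinical progression prior to post-baseline tumor assessments".

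Section 1.4 sets the ceiling: "Up to 25 subjects will be enrolled to target 21 evaluable patients". It also ties the end of accrual to 21 subjects who were dosed and finished one cycle, which is a further criterion.

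The protocol foresees patients who fail without a scan. The end-of-treatment note in the Section 10 calendar provides for an early visit "or if the patient cannot return due to disease progression". Appendix B has a category for "Subjects with a global deterioration of health status requiring discontinuation of treatment without objective evidence of disease progression at that time".

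**The concern.** Sections 11.1 and 13.1 define the same analysis set differently. A patient who stops for clinical progression before any scan is evaluable under 13.1 and a non-responder for ORR under 11.2, but falls among the other reasons in 11.1 and is replaced. A patient who dies of disease before the first scan is named in none of the four rules.

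The C2D1 limit in 11.1 can be read in two ways:

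- If it limits only withdrawal and loss to follow-up, any unscanned clinical progression or death up to the first scan is replaced.
- If it limits the whole sentence, replacement closes at about day 29, and 11.1 has no rule for unscanned failure between then and the scan at week 8.

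Either way, 11.1 drops some patients because they did badly. In a single-arm trial that stops at 0 of 7 and rejects at 3 of 21, this raises the estimated DCR, weakens the futility look, and lets the denominator be chosen after outcomes are known.

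A smaller point is that 13.2 restricts PFS and OS to evaluable individuals who had at least one dose. That could mean all dosed patients, or it could import the scan-based definition.

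**Working it through.** **Inputs from 13.1 and 1.4.** Null DCR 5%, alternative 30%; 7 patients in stage 1, stop at 0 successes; 14 more for 21; reject at 3 or more; stated type I error 0.064 (target 0.1), power 90%, early stopping 70%; enrolment cap 25.

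**Assumed input.** f is the share of treated patients who fail by clinical progression or death with no post-baseline scan and are replaced. The documents do not give it; the range used is 5% to 30%. The plan's allowance of 4 in 25 (16%) is a reference point only. The median PFS of 1.5 months cited in 13.1 is shorter than the 8 weeks to the first scan, but does not show how many patients would go unscanned.

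**Step 1: reproduce the plan's figures.** With X1 ~ Bin(7, p) and X2 ~ Bin(14, p):

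- Early stopping at p = 0.05: 0.95^7 = 0.6983.
- Type I error: P(X1=1)·P(X2≥2) + P(X1=2)·P(X2≥1) + P(X1≥3) = 0.2573×0.1530 + 0.0406×0.5123 + 0.0038 = 0.0639.
- The same formula at p = 0.30 gives power 0.904.

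All three agree with the stated values. The design arithmetic is sound; the fault lies in who enters it.

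**Step 2: apply 11.1 as written.** Each treated patient is a success (probability 0.05), an unscanned failure who is replaced (f), or an evaluable failure (0.95 − f). Among analysed patients the success probability becomes 0.05/(1 − f); for example 0.05/0.84 = 0.0595 at f = 16%. The trial stops at 0 successes in the first 7 evaluable, otherwise runs to 21 evaluable or 25 treated, and rejects at 3 or more successes, including when the cap leaves fewer than 21 evaluable. The calculation is an exact recursion, not a simulation.

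| f (assumed) | Type I error, cap 25 | Early stopping at 5% | Type I error, no cap |
|---|---|---|---|
| 0 | 0.0639 | 0.6983 | 0.0639 |
| 5% | 0.0721 | 0.6849 | 0.0721 |
| 10% | 0.0808 | 0.6702 | 0.0818 |
| 16% | 0.0902 | 0.6508 | 0.0957 |
| 20% | 0.0952 | 0.6365 | 0.1068 |
| 25% | 0.1002 | 0.6170 | 0.1230 |
| 30% | 0.1043 | 0.5953 | 0.1426 |

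With the cap, type I error reaches 0.10 at f = 0.248. The last column is for comparison only, since 1.4 caps enrolment at 25. If the C2D1 limit covers the whole sentence in 11.1, f counts only failures in the first cycle.

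**Step 3: effect on the estimate.** Take 3 successes with 4 unscanned failures replaced. The report reads 3/21 = 14.3% (exact 95% CI 3.0% to 36.3%). With those 4 counted it is 3/25 = 12.0% (2.5% to 31.2%).

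**Step 4: the other reading.** If 13.1 governs and its evaluable progressors are scored as failures, clinical progressors stay in the denominator and f shrinks to deaths before the first scan. If those deaths also count as failures, f = 0 and the stated figures hold.

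**The case against.** Three of the four statements name clinical progression, and 11.1 matches the ORR wording in 11.2 except for that phrase. It may simply have been dropped, and a sensible analyst would follow 13.1. The plan also tries to obtain scans: the Section 10 calendar calls for CT at end of treatment, 28 days ± 4 weeks after the last dose, and Appendix B asks for every effort to document progression after treatment stops. Entry requires ECOG 0 or 1 and life expectancy above 3 months. All this points to a small f.

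The inflation is modest too. From f = 5% to 20%, type I error stays inside the plan's 10% target. It also depends on rejecting with fewer than 21 evaluable, on which 13.1 is silent; if all 21 were required, type I error would be 7.4% at f = 10% and 6.0% at 16%. In the example, 3/21 and 3/25 both contain 3 successes, and the intervals overlap almost completely. If early failures were evaluable, accrual would end at 21 evaluable, so 3/25 is not the result that 13.1 would produce.

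These points stand as limits on size. They do not remove the contradiction: no text gives 13.1 precedence, the section that defines the primary endpoint is the one that differs, and 13.1 itself leaves out early death. The PFS and OS point is minor, since both sentences refer to dosing and both endpoints count death as an event.

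**Conclusion.** The concern holds. Sections 11.1 and 13.1 give different denominators for the primary endpoint, and no DCR or ORR evaluability rule covers death before the first scan. It must be settled before outcomes are known, because the denominator and the stage 1 decision are undefined as written. That reason does not depend on any assumed rate.

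The bias is conditional. It arises if 11.1 is applied as written, and its size depends on an f that the documents do not give. With the cap of 25 and rejection allowed below 21 evaluable, type I error rises from 6.4% to between 7.2% and 10.4% for f of 5% to 30%. Early stopping at a 5% DCR falls from 69.8% to between 68.5% and 59.5%. Under 13.1 most of this disappears.

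**What to change.** 1. Align 11.1 with 13.1: a dosed patient with toxicity discontinuation, clinical progression or death from any cause before the first post-baseline scan is evaluable and counts as a failure.
2. Limit replacement to patients never dosed, or who withdraw or are lost before C2D1 with no evidence of progression or death. State that the C2D1 limit applies to all replacement.
3. Add a sensitivity analysis of all dosed patients that counts replaced dosed patients as failures.
4. Reword the accrual sentence in 1.4 to use this definition of evaluable instead of completion of one cycle.
5. State that PFS and OS are analysed in all dosed patients.

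The cost is protocol and SAP wording only; design and sample size stay the same. The observed DCR may be slightly less favourable, and fewer patients can be replaced.

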11.2 Secondary Endpoints

The secondary endpoints are as follows:

- ORR is defined as the proportion of subjects with PR or CR according to RECIST 1.1. Subjects who discontinue due to toxicity or clinical progression prior to post-baseline tumor assessments will be considered as non-responders. Otherwise, subjects who discontinue or do not have any post-baseline scans for other reasons including withdrawal of consent or being lost to follow-up prior to C2D1 will be replaced and not included in the primary efficacy analysis.
- Progression-free survival (PFS) is defined as the number of months from the first
 dose of retifanlimab to radiographic disease progression (PD or relapse from CR
 as assessed using RECIST 1.1 criteria), documented clinical progression as
 assessed by the treating provider, or death due to any cause. PFS will be censored
 at the date of the last scan for subjects without documentation of disease
 progression at the time of analysis.
- Safety assessed by the following measures:
 - Number of patients who have grade 3 or above drug-related toxicities
 - Frequency of drug-related toxicity by grade
 - Retifanlimab-related infusion reactions
 - Immune-related AEs
 - Unacceptable toxicities
 - Vital signs: BP, pulse, temperature
 - Physical examination
 - Changes in ECG readings
 - Clinical hematology: complete blood count (CBC) with differential ANC,
 ALC, AEC, and platelet count
 - Clinical serum chemistry: sodium, potassium, chloride, bicarbonate, glucose, blood urea nitrogen (BUN), creatinine, lactate dehydrogenase (LDH), ALT, AST, alkaline phosphatase, lipase, bilirubin (total), total protein, albumin, calcium, magnesium and phosphate

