11.3 Exploratory Endpoints

- OS, DOR, TTP.
 - Overall survival (OS) is defined as the number of months from the first dose of retifanlimab until death or end of follow-up (OS will be censored on the date the subject was last known to be alive for subjects without documentation of death at the time of analysis).
 - Duration of Response (DOR) is defined as the number of months from the first documentation of a response to date of disease progression.
 - Time to-progression (TTP) is defined as the number of months from the first dose of retifanlimab to the date of documented disease progression (PD or relapse from CR as assessed using RECIST 1.1 criteria). It differs from PFS in that it does not include death in the definition of an event. TTP will be censored at the date of the last scan for subjects without documentation of disease progression at the time of analysis.
 - Disease control rate (DCR) is defined as the proportion of subjects with complete response, partial response and stable disease
- Disease control rate, objective response rate, progression-free survival, and duration of response measured by iRECIST
- Immune subset analyses by IHC, next generation sequencing and gene expression profiling of tumor tissue
- Immune subset analyses in PBMCs including effector, helper, and regulatory T cells, NK cells, and macrophages
- Circulating cytokine analysis in patient sera
- Immune checkpoint analysis by IHC and gene expression profiling
- Tumor marker kinetics measured by change in serum CA19-9 concentrations from baseline

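### Section 11.2 contradicts itself on whether a death without documented progression is a PFS event, and it omits the new-therapy censoring rule in 13.2

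*Combined protocol and SAP*

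**What the plan says.** **Section 11.2, events and censoring.** PFS runs from first dose to radiographic progression, clinical progression documented by the provider, or death. The event list and the censoring sentence adjoin: "assessed by the treating provider, or death due to any cause. PFS will be censored". The censoring then applies "at the date of the last scan for subjects without documentation of disease" progression at the time of analysis. It makes no exception for death and does not mention new therapy.

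**Section 11.3, TTP.** "TTP will be censored at the date of the last scan for subjects without documentation of disease progression at the time of analysis". Only the endpoint name differs from the PFS sentence. On the contrast between the two endpoints, 11.3 says: "It differs from PFS in that it does not include death in the definition of an event".

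**Section 13.2, PFS analysis.** The endpoint runs "until first documented local progression or death due to any cause". A further rule follows: "Individuals will be censored at the date of the last scan prior to initiation of an alternative therapy for PFS", with the condition "if no event occurs before the start of the alternative therapy".

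**Follow-up.** Under 1.4 and 5.12.2, disease imaging ends when a new antineoplastic therapy starts. Under 1.4, contact continues until death, and survival and new therapies are recorded. No section says whether 11.2 or 13.2 governs PFS.

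**The concern.** Two kinds of subject are classified differently depending on which sentence the analyst follows.

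1. A subject who dies with neither radiographic nor clinical progression documented. The 11.2 definition gives an event at death. The 11.2 censoring sentence, taken literally, gives censoring at the last scan. If the death precedes the first 8-week scan, the last scan is the baseline one and the subject contributes essentially nothing to the curve. For these subjects PFS would become TTP.
2. A subject who stops without progression, starts another therapy and later dies. The 11.2 definition gives an event. Section 13.2 censors before the new therapy.

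PFS is a secondary objective (1.2.2). With 21 evaluable patients and no comparator, a few reclassified subjects visibly change the curve, and a choice left open can be made after the data are seen.

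**Working it through.** **Step 1. The plan's own figures.** The only design calculation is the Simon two-stage design for DCR in 13.1: 7 patients, stop at 0; 21 in total, reject at 3 or more.

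- P(reject) = sum over x = 1 to 7 of P(X1 = x) × P(X2 ≥ 3 − x), with X1 ~ Bin(7, p) and X2 ~ Bin(14, p).
- p = 5%: 0.0639 (stated 0.064). p = 30%: 0.904 (stated 90%). Early stop at 5%: 0.95^7 = 0.698 (stated 70%).

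These reproduce, and none of them uses PFS. Section 13.2 gives PFS no test, threshold or event target.

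**Step 2. The rules side by side.**

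| Subject | 11.2 definition | 11.2 censoring sentence, literal | 13.2 |
|---|---|---|---|
| Dies, no documented progression, no new therapy | Event at death | Censored at last scan | Event at death |
| New therapy without progression, then dies | Event at death | Censored at last scan | Censored at last scan before new therapy |
| Alive, no progression, no new therapy | No event | Censored at last scan | No event |

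The readings part only on the first two rows.

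**Step 3. Size for the first row alone.** Assumptions: exponential PFS; a share d of first events are deaths without documented progression; progression is seen at once. Censoring those deaths leaves hazard (1 − d)·ln2/m, so the median becomes m/(1 − d) and PFS at t becomes 0.5^(t(1 − d)/m). The value m = 1.5 months is the pancreatic adenocarcinoma figure cited in 13.1; d has no source in the documents.

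| d | Median (months) | 4-month PFS |
|---|---|---|
| Deaths counted | 1.50 | 15.7% |
| 10% censored | 1.5/0.9 = 1.67 | 18.9% |
| 20% censored | 1.5/0.8 = 1.88 | 22.8% |
| 30% censored | 1.5/0.7 = 2.14 | 27.4% |

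**Step 4. The same with 8-week scans and n = 21.** In 2,000 simulated trials per setting, progression is dated at the next scan. At d = 20% the mean Kaplan-Meier median goes from 2.1 to about 2.55 months and 4-month PFS from 18% to 23%. At 10% the changes are 2.2 to 2.4 months and 18% to 20%; at 30%, 2.1 to 2.8 months and about 18% to 27%. The median mostly falls on a scan date, so both rules give the same median in about 89%, 74% and 57% of trials at 10%, 20% and 30%. The between-trial standard deviation of 4-month PFS is about 8 points with deaths counted.

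**Step 5. Both rows together, invented data.** There are 21 subjects:

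- 12 progressions: 6 at 1.84 months, 4 at 3.68, 2 at 5.52.
- 4 deaths without progression, at 1.0, 1.5, 2.8 and 3.3 months.
- 3 subjects with last scan at 1.84 months, new therapy at 2.5, and death at 6, 7 and 8.
- 2 ongoing at 7.36 months.

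6-month Kaplan-Meier PFS:

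- 11.2 definition: (20/21)(19/20)(13/19)(12/13)(11/12)(7/11)(5/7)(4/5) = 19.0%.
- 11.2 censoring sentence, literal: (13/19)(4/8)(2/4) = 17.1%.
- 13.2: (20/21)(19/20)(13/19)(9/10)(8/9)(4/8)(2/4) = 12.4%.

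| Reading | Events | Median (months) | 4-month PFS | 6-month PFS |
|---|---|---|---|---|
| 11.2 definition | 19 | 3.68 | 33.3% | 19.0% |
| 11.2 censoring sentence, literal | 12 | 3.68 | 34.2% | 17.1% |
| 13.2 | 16 | 3.30 | 24.8% | 12.4% |

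The literal sentence raises 4-month PFS and lowers 6-month PFS against the definition, so the direction is not fixed.

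**The case against.** The best defence is that the intent is plain. Sections 11.2 and 13.2 both name death as an event, and 11.3 separates TTP from PFS on exactly that ground. Censoring ordinarily applies only to subjects with no event, so a careful statistician would count the deaths. A reader might infer that the plan directs deaths to be censored; the documents do not support that. What remains is that the 11.2 sentence, followed as written, does the opposite of the definition beside it. The overall survival rule in 11.3 limits censoring to subjects without a documented death, and the PFS rule has no such limit.

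Section 13.2 can also be read as the detailed special case of a general rule in 11.2. That is reasonable, but neither section says so. Because protocol imaging stops at new therapy, the last scan will usually be the same scan under both sections. The censoring date is therefore a thin difference; whether a later death counts is not.

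On size, provider-documented clinical progression is also an event. Many patients who deteriorate between scans would be events before death, which shrinks the affected group. The calculations in steps 3 and 4 do not model this, and the 10% to 30% range is assumed. At d = 20% the simulated 4-month shift, about 5 points, is below the between-trial standard deviation. A shift from the choice of rule is nonetheless systematic and does not average out as sampling noise does.

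**Conclusion.** The point holds as an internal contradiction in 11.2 and an omission relative to 13.2. It is a wrongly worded rule, since the definition and the censoring sentence cannot both be applied to a subject who dies without documented progression.

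The size is conditional. With a 1.5-month true median and 10% to 30% of first events being such deaths, censoring them moves the exponential median from 1.50 to between 1.67 and 2.14 months, and 4-month PFS from 15.7% to between 18.9% and 27.4%. The share is an assumption, and clinical progression would reduce it. If no subject dies without documented progression and none has an event after starting new therapy, the readings agree.

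A reader might infer that reported PFS will be inflated or that the trial's main conclusion is at risk. Neither follows. The invented data show movement in both directions, and PFS is a descriptive secondary endpoint. DCR, the 21 evaluable patients, the 0.064 type I error and the 90% power are untouched.

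**What to change.** Replace the 11.2 censoring sentence with:

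> Subjects with neither progression (radiographic or documented clinical) nor death are censored at the last scan. Subjects with no event before the start of an alternative therapy are censored at the last scan before that therapy, whatever happens later (as in 13.2). Death without prior documented progression and before any alternative therapy is an event at the date of death.

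The second sentence must not be limited to subjects who are alive. Otherwise a death after new therapy would become an event in 11.2 while 13.2 still censors that subject, and the conflict would stay open. The TTP sentence in 11.3 can remain, since leaving deaths out is intended there.

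The cost is three sentences in one section. The event definition and the new-therapy rule are the sponsor's own. New-therapy and survival data are already collected, and no design figure changes. The change should be made before PFS is analysed, so that the choice of rule does not depend on the data.
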